Following induction therapy in the Neoadjuvant Atezolizumab Therapy Phase, patients will undergo surgical resection of the primary tumor and associated lymph nodes.

Repeat chest CT scan, PET/CT scan, and MRI of the brain will be obtained prior to surgical resection and collected for review.

Resection may be accomplished via an open or minimally invasive procedure (i.e., thoracotomy, sternotomy, clamshell or hemiclamshell incisions; or video assisted thoracic surgery (VATS) or robotically assisted VATS.

Pathologic complete resection of the primary tumor (R0) should be performed. Anatomic resection via segmentectomy, lobectomy, bilobectomy or pneumonectomy is strongly preferred although wedge resection is acceptable for very small (2 cm or less) tumors located peripherally where wedge resection permits a wide margin (at least 1 cm in all directions).

Hilar and mediastinal lymph node dissection or sampling should be performed. For right sided resections, this involves at least lymph nodes from levels 4R, 7, 10R, and 11R. For left sided resections, this involves at least lymph nodes from levels 5/6, 7, 10L, and 11L. Patients in whom a complete resection is not achieved will be discontinued from the study and will be replaced.

Pathologic specimens will undergo standard histopathologic and immunohistochemical evaluation for lung cancer. Tumor, normal lung parenchyma, and draining lymph nodes will be harvested immediately after resection. Sections of tumor will be fresh frozen and formalin-fixed for correlative studies. Sections of lymph nodes will be freshly prepared in media and formalin-fixed for correlative studies. Sections of adjacent normal lung tissue will be formalin-fixed for correlative studies. Sections of tumor, adjacent normal lung tissue, and lymph node may be freshly dissociated for correlative studies.

Whole blood samples will be collected at the time of surgical resection for correlative studies. The blood will be used for IMMUNOME and processed for PBMC, plasma, and serum for correlative studies.

At the postoperative follow-up visit, patients whose tumors have not demonstrated evidence of pathologic response or who have radiographic progression will have an end-of-study treatment (atezolizumab) visit, after which they will enter Surveillance for 2 years then Survival Follow-up for 1 year.

Whole blood will be collected at postoperative follow-up visit and will be processed for plasma, serum, and PBMC for correlative studies.

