Surveillance

All patients who undergo surgery will enter the Surveillance Period. During Surveillance, patients will be monitored by extended chest CT scans (including liver and adrenals). Whole blood will be collected for plasma and serum, and PBMCs (at selected timepoints) every 6 weeks to 3 months for 2 years for correlative studies. Upon completion of Surveillance, patients enter Survival Follow-up. Patients whose disease progresses or recurs during Surveillance will discontinue from Surveillance and enter Survival Follow-up.

For patients previously enrolled under Protocol Version 3 or earlier:

- If the patient re-consents under Protocol Version 4 > 3 months after the Post-surgery Visit: patient will not enter Surveillance and will follow the schedule of activities from Protocol Version 3.

Atezolizumab—Genentech, Inc.

14/Protocol ML39236, Version 7

- If the patient re-consents under Protocol Version 4 at any time between Screening and the Post-surgery Visit: patient will be offered to enter Surveillance and follow Protocol Version 4 schedule of activities.
- If the patient re-consents under Protocol Version 4 \leq 3 months after the Post-surgery Visit: patient will be offered to enter Surveillance and follow Protocol Version 4 schedule of activities only if post-surgery baseline chest CT scan is available. If chest CT scan is not available, patient will follow the schedule of activities from Protocol Version 3.

Adjuvant Atezolizumab Therapy Phase

Patients whose tumors have evidence of pathologic response or lack of radiographic progression will be eligible for the Adjuvant Atezolizumab Therapy Phase, which will occur during the Surveillance period.

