- Treatment with an investigational agent for any condition within 4 weeks prior to Cycle 1, Day 1 (or within five half-lives of the investigational product, whichever is longer)
- History of severe allergic, anaphylactic, or other hypersensitivity reactions to chimeric or humanized antibodies or fusion proteins
- Pregnant or lactating, or intending to become pregnant during the study

- Women of childbearing potential must have a negative serum pregnancy test result within 7 days prior to initiation of atezolizumab.

Adjuvant Atezolizumab Therapy Phase

- Progressive or recurrent disease as documented by CT (per RECIST v1.1 criteria) at the end of SOC adjuvant therapy
 - Patients with radiographic progression and no evidence of pathologic response of the study during the neoadjuvant phase are not eligible for the Adjuvant Atezolizumab Therapy Phase.

End of Study

The end of this study is defined as the date when the last data point required for survival follow-up is received from the last patient. This is expected to occur approximately 3 years after the last patient receives the last dose of adjuvant atezolizumab.

The Neoadjuvant Atezolizumab Therapy Phase will end when the last data point required for primary efficacy analysis (i.e., pathology evaluation at time of surgery) is obtained. This is expected to occur approximately 30 days after the last patient's surgery.

The Surveillance period will end 2 years after the post-surgery visit.

After completing neoadjuvant or adjuvant treatment with atezolizumab, patients will be followed for survival for up to 3 years. For patients that undergo surgery and enter Surveillance, time in surveillance will overlap with time in survival follow-up.

Length of Study

The total length of the study, from screening of the first patient to the end of the study, is expected to be approximately 6 years.

Investigational Medicinal Products

Test Product (Investigational Drug)

The investigational medicinal product (IMP) for this study is atezolizumab.

The dose of atezolizumab in this study will be 1200 mg administered by IV infusion q21d (one cycle=21 days).

In the Neoadjuvant Atezolizumab Therapy Phase, neoadjuvant treatment with atezolizumab 1200 mg will be given q21d (\pm 2 days) for a maximum of 2 cycles. In the Adjuvant Atezolizumab Therapy Phase, adjuvant treatment with atezolizumab 1200 mg will be given q21d (\pm 3 days) for maximum of 12 months.

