The Neoadjuvant Atezolizumab Therapy Phase will only include patients with Stage IB, II, IIIA, or selected IIIB disease and who are deemed suitable for surgical resection without metastatic disease but with sufficient material for initial biopsy to analyze biomarkers. Clinical staging of NSCLC is based on computed tomography (CT) of the chest and upper abdomen, positron emission tomography (PET) and brain CT or magnetic resonance imaging (MRI) to rule out metastatic disease and assess the potential for curative-intent resection. Resection represents the best chance for prolonged survival for patients with non-advanced NSCLC.

After surgical resection, routine clinical surveillance will involve repeated radiographic imaging and monitoring of clinical symptoms for disease recurrence. All patients that complete surgical resection, will be monitored for disease recurrence using extended CT scans with IV contrast every 6 weeks to 3 months. Blood samples will be obtained along with chest CT scans to explore the association of blood-based biomarkers, such as ctDNA positivity with clinical outcome, for up to 2 years. Early detection of biomarkers that predict relapse of disease may help identify personalized treatment options to limit disease recurrence for patients in the future. Blood-based assay approaches, such as detection of circulating tumor DNA (ctDNA), may represent an innovative tool to complement disease surveillance in NSCLC.

Following resection, the risk for relapse correlates with clinical and pathological stage, but the addition of cisplatin based adjuvant chemotherapy improves survival for patients with Stage II and IIIA disease (Pignon et al. 2008), and potentially for some Stage IB patients with lesions greater than 4 cm (Butts et al. 2010).

Therefore, this study will also include a second (exploratory) part, the Adjuvant Atezolizumab Therapy Phase, which will enroll patients who demonstrated clinical benefit (defined as evidence of pathologic response or absence of radiographic progression) with neoadjuvant atezolizumab, to receive up to 12 additional months of adjuvant atezolizumab. Patients can choose to receive standard-of-care (SOC) adjuvant

chemotherapy (with or without radiation) before receiving atezolizumab post-surgical resection.

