Hilar and mediastinal lymph node dissection or sampling should be performed. For right sided resections, this involves at least lymph nodes from levels 4R, 7, 10R, and 11R. For left sided resections, this involves at least lymph nodes from levels 5/6, 7, 10L, and 11L. Patients in whom a complete resection is not achieved will be discontinued from the study and will be replaced.

Pathologic specimens will undergo standard histopathologic and immunohistochemical evaluation for lung cancer. Tumor, normal lung parenchyma, and draining lymph nodes will be harvested immediately after resection. Sections of tumor will be fresh frozen and formalin-fixed for correlative studies (see [Appendix 3](#)). Sections of lymph nodes will be freshly prepared in media and formalin-fixed for correlative studies. Sections of adjacent normal lung tissue will be formalin-fixed for correlative studies. Sections of tumor, adjacent normal lung tissue and lymph node may be freshly dissociated for correlative studies.

Whole blood samples will be collected at the time of surgical resection for correlative studies. The blood will be used for IMMUNOME and processed for PBMC, plasma, and serum for correlative studies.

At the postoperative follow-up visit, patients whose tumors have not demonstrated evidence of pathologic response or who have radiographic progression will have an end-of-study treatment (atezolizumab) visit, after which they will enter Surveillance for 2 years then Survival Follow-up for 1 year.

Whole blood will be collected at postoperative follow-up visit and will be processed for plasma, serum, and PBMC for correlative studies.

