3.1.4 Adjuvant Atezolizumab Therapy Phase

Patients whose tumors have evidence of pathologic response or lack of radiographic progression will be eligible for the Adjuvant Atezolizumab Therapy Phase, which will occur during the Surveillance period.

During this part of the study, patients will receive adjuvant atezolizumab for up to a maximum of 12 additional months (up to 18 cycles). Adjuvant atezolizumab treatment may be started directly after surgery or after adjuvant SOC chemotherapy (with or without radiation). Choice of adjuvant SOC chemotherapy will be at the discretion of the treating physician, depending on the disease stage, as deemed clinically appropriate. It is highly recommended that any adjuvant treatment be initiated within 120 days after surgery. Additionally, it is recommended that patients who receive SOC Chemotherapy (\pm Radiotherapy) initiate adjuvant atezolizumab within 60 days of SOC Chemotherapy \pm Radiotherapy (whichever occurs last). If adjuvant treatment is planned to start outside of the recommended window, *Investigators may discuss it with the Medical Monitor.*

Whole blood samples will be collected prior to infusion on adjuvant Cycle 1, Day 1. Subsequent blood samples will be collected during Surveillance (see Section 3.1.3) and 30 days after the last dose for correlative studies. The blood will be processed for PBMC, plasma, and serum.

Optional bronchial brushings samples may be collected from patients undergoing bronchoscopy or EBUS at prescreening or screening and approximately 3–4 months after starting adjuvant atezolizumab treatment (Group D only).

For all patients whose disease progresses or recurs (confirmed by imaging) at any time between neoadjuvant treatment and surveillance may undergo an optional tissue biopsy (tumor and lymph node, if available) for correlative studies, which will require a separate ICF signature (see Section 4.5.1). A blood sample will also be collected at the time of disease progression/recurrence.

All patients will enter Survival Follow-up, which will cover new anti-cancer treatment, DFS, and OS for up to 3 years after the last dose of atezolizumab (See [Appendix 2](#) for details regarding time in Survival Follow-up).

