- History of severe allergic, anaphylactic, or other hypersensitivity reactions to chimeric or humanized antibodies or fusion proteins
- Pregnant or lactating, or intending to become pregnant during the study
 - Women of childbearing potential must have a negative serum pregnancy test result within 7 days prior to initiation of atezolizumab

Adjuvant Atezolizumab Therapy Phase

- Progressive or recurrent disease as documented by CT scan (per RECIST v1.1 criteria) at the end of SOC adjuvant therapy
 - Patients with radiographic progression/recurrence and no evidence of pathologic response of the study during the Neoadjuvant Phase are not eligible for the Adjuvant Atezolizumab Therapy Phase

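### Protocol Section 3.1.2 takes a patient with neither pathologic response nor radiographic progression off atezolizumab, while Section 3.1.4 makes that patient eligible for adjuvant atezolizumab and Section 4.1.2 does not exclude them

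*Protocol*

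**What the plan says.** Section 3.1.2 of the protocol, in its surgical resection text, sets this rule for the check after surgery: "patients whose tumors have not demonstrated evidence of pathologic response or who have radiographic progression will have an end-of-study treatment (atezolizumab) visit". Those patients then go through 2 years of Surveillance and 1 year of Survival Follow-up. The synopsis applies the same rule to "patients whose tumors have not demonstrated evidence of pathologic response or who have radiographic progression".

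Section 3.1.4 sets the adjuvant rule: "Patients whose tumors have evidence of pathologic response or lack of radiographic progression will be eligible" for the adjuvant phase. Section 1.3 describes the adjuvant cohort as those who "demonstrated clinical benefit (defined as evidence of pathologic response or absence of radiographic progression) with neoadjuvant atezolizumab". The synopsis, Section 3.1.1 and SAP Sections 1.3 and 3.1 use the same definition. Section 4.1.1 adds ECOG and laboratory conditions.

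Section 4.1.2 denies adjuvant treatment on neoadjuvant outcome to "Patients with radiographic progression/recurrence and no evidence of pathologic response"; the synopsis has "Patients with radiographic progression and no evidence of pathologic response of the study during the neoadjuvant phase are not eligible". A separate exclusion covers a later time point: "Progressive or recurrent disease as documented by CT scan (per RECIST v1.1 criteria) at the end of SOC adjuvant therapy".

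Section 4.6.2 lists the reasons for which atezolizumab must be stopped. Progression, as judged by the investigator, is on the list. Lack of pathologic response is not.

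**The concern.** The postoperative visit is where a site decides whether a patient goes on to adjuvant drug. The instruction for that visit ends atezolizumab if either of two conditions is met. The eligibility text withholds drug only if both are met. A site that follows Section 3.1.2 literally would withhold up to 12 months of study drug from a patient whom Section 3.1.4 admits, while another site working from Sections 3.1.4 and 4.1.2 could treat the same kind of patient. Entry to the adjuvant phase would then depend partly on which section a site reads.

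**Working it through.** No stated figure needs reproducing; the check is logical. Let R be evidence of pathologic response and P be radiographic progression.

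- Section 3.1.2 and synopsis, end of atezolizumab: (not R) or P.
- Section 3.1.4 and the clinical-benefit definition, eligible: R or (not P).
- Section 4.1.2, excluded on neoadjuvant outcome: P and (not R).

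| R | P | 3.1.2 | 3.1.4 | 4.1.2 | Result |
|---|---|---|---|---|---|
| yes | no | not ended | eligible | not excluded | consistent |
| no | no | ended | eligible | not excluded | **conflict** |
| yes | yes | ended | eligible | not excluded | differs; see objection |
| no | yes | ended | not eligible | excluded | consistent |

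The complement of R or (not P) is (not R) and P. Section 4.1.2 states that complement correctly. Section 3.1.2 and the synopsis join the same two conditions with *or*, which produces the second row.

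**Could the visit merely close the neoadjuvant course?** No. Appendix 1, footnote e, places the discontinuation visit of a patient who will receive adjuvant atezolizumab at the end of adjuvant treatment. The 1 year of Survival Follow-up in Section 3.1.2 is also the Group A figure (no adjuvant treatment) in Appendix 2, Table 1; Group B has 2 years in Table 2.

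**What changes for one affected patient who would otherwise have received adjuvant drug:**

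- Exposure: 0 adjuvant doses against up to 18 (Section 3.1.4; Appendix 1 gives a maximum of 17).
- Safety collection (Section 5.3.1, Table 5), without adjuvant drug and with the second neoadjuvant dose on Day 22: AEs to 22 + 30 = Day 52; SAEs and AESIs to 22 + 90 = Day 112.
- Safety collection with adjuvant drug alone, assuming surgery on Day 40 and a start 28 to 120 days later (Day 68 to Day 160). One dose on Day 68 gives 68 + 30 = Day 98 and 68 + 90 = Day 158. Eighteen doses from Day 160 put the last at 160 + 17 × 21 = Day 517, giving 517 + 30 = Day 547 and 517 + 90 = Day 607.
- Subgroup: A instead of B, or C instead of D, which alters the disposition summary in SAP Section 6.2.1.
- Survival Follow-up after Surveillance: 1 year against 2 for Group B. Group D is unclear, because Appendix 2, Table 4 counts 3 years from the last neoadjuvant dose while its footnote a counts from the last atezolizumab dose.

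**The case against.** The best reply is that the intent is plain. Section 3.1.2 assigns a visit and a follow-up path and never calls the patient ineligible. The sections written to govern eligibility, exclusion and discontinuation all point the other way, and the clinical-benefit definition repeats the eligibility rule in both documents. A site checking eligibility would probably use those sections, and *or* is probably a slip for *and*. This supports the direction of the correction. It does not remove the conflict: the wording appears twice, it is mandatory, and it sits in the instruction for the visit at which the decision is taken.

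It is also fair that the day counts and follow-up lengths are consequences rather than further errors. The shorter collection window is what Table 5 intends for a patient off drug, and the follow-up difference arises because follow-up is tied to the last dose. The days rest on assumptions: Section 4.6.2 allows surgery after one neoadjuvant dose, the 120-day start is only a recommendation, and doses may be held. Day 547 and Day 607 are not upper limits.

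A reader might infer from the third row that atezolizumab should simply stop when a patient with pathologic response shows progression, and that Section 3.1.2 should say so. The documents do not settle this. Section 3.1.4 makes that patient eligible and Section 4.1.2 does not exclude them on neoadjuvant outcome, while Section 4.6.2 requires stopping for progression on the investigator's integrated assessment of imaging, biopsy and clinical status. A flat stop on confirmed progression would contradict Section 3.1.4 and use a standard absent from Section 4.6.2.

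**Conclusion.** The contradiction is real for the patient with no pathologic response and no progression, and it should be corrected. Section 4.1.2 does not itself make this patient eligible; it fails to exclude them. Eligibility comes from Section 3.1.4, subject to the ECOG and laboratory criteria, and being eligible does not mean being treated.

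The number affected cannot be stated. A reader might equate evidence of pathologic response with major pathologic response. If all 180 patients had surgery, rates of 5% to 15% would leave 180 − 9 = 171 down to 180 − 27 = 153 without response, suggesting that most of the trial is caught. The documents do not support that: Appendix 5 defines only major response, no threshold is given for evidence of response, and the count would include patients with progression. Under a looser threshold the group would be smaller.

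The effect is confined to adjuvant exposure and its consequences in a phase the protocol calls exploratory. The primary test rests on pathology at surgery, so it, the sample size and the futility rule do not change. SAP Section 6.3.3 splits OS, DFS and EFS by major pathologic response and PD-L1 status, not by Subgroups A to D. Protocol Figures 1 and 2 were not available for this check and may bear on postoperative routing.

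**What to change.** In Section 3.1.2 and in the matching synopsis sentence, change *or* to *and* before the clause on radiographic progression. The rule then reads (not R) and P, which equals the Section 4.1.2 exclusion on neoadjuvant outcome and is the exact complement of Section 3.1.4. The three sections then agree in all four rows of the table.

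Add no stopping sentence for the patient with both response and progression. The sponsor should decide that case separately, reconciling Section 3.1.4 with the investigator assessment in Section 4.6.2.

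The cost is one word in each of two sentences and a clarification to sites. No statistical change is needed.

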3.1.3 Surveillance

All patients who undergo surgery will enter the Surveillance Period. During Surveillance, patients will be monitored by extended chest CT scans (including liver and adrenals). Whole blood will be collected for plasma and serum, and PBMCs (at selected timepoints), every 6 weeks to 3 months for 2 years for correlative studies (see [Appendix 2](#) for details). Upon completion of Surveillance, patients enter Survival Follow-up. Patients whose disease progresses or recurs during Surveillance will discontinue from Surveillance and enter Survival Follow-up.

For patients previously enrolled under Protocol Version 3 or earlier:

- If the patient re-consents under Protocol Version 4 >3 months after the Post-surgery Visit: patient will not enter Surveillance and will follow the schedule of activities from Protocol Version 3 (see [Appendix 11](#)).
- If the patient re-consents under Protocol Version 4 at any time between Screening and the Post-surgery Visit: patient will be offered to enter Surveillance and follow Protocol Version 4 schedule of activities.
- If the patient re-consents under Protocol Version 4 ≤ 3 months after the Post-surgery Visit: patient will be offered to enter Surveillance and follow Protocol Version 4 schedule of activities only if post-surgery baseline chest CT scan is available. If chest CT scan is not available, patient will follow the schedule of activities from Protocol Version 3 (see [Appendix 11](#)).

3.1.4 Adjuvant Atezolizumab Therapy Phase

Patients whose tumors have evidence of pathologic response or lack of radiographic progression will be eligible for the Adjuvant Atezolizumab Therapy Phase, which will occur during the Surveillance period.

During this part of the study, patients will receive adjuvant atezolizumab for up to a maximum of 12 additional months (up to 18 cycles). Adjuvant atezolizumab treatment may be started directly after surgery or after adjuvant SOC chemotherapy (with or without radiation). Choice of adjuvant SOC chemotherapy will be at the discretion of the treating physician, depending on the disease stage, as deemed clinically appropriate. It is highly recommended that any adjuvant treatment be initiated within 120 days after surgery. Additionally, it is recommended that patients who receive SOC Chemotherapy (\pm Radiotherapy) initiate adjuvant atezolizumab within 60 days of SOC Chemotherapy \pm Radiotherapy (whichever occurs last). If adjuvant treatment is planned to start outside of the recommended window, *Investigators may discuss it with the Medical Monitor.*

Whole blood samples will be collected prior to infusion on adjuvant Cycle 1, Day 1. Subsequent blood samples will be collected during Surveillance (see Section 3.1.3) and 30 days after the last dose for correlative studies. The blood will be processed for PBMC, plasma, and serum.

Optional bronchial brushings samples may be collected from patients undergoing bronchoscopy or EBUS at prescreening or screening and approximately 3–4 months after starting adjuvant atezolizumab treatment (Group D only).

For all patients whose disease progresses or recurs (confirmed by imaging) at any time between neoadjuvant treatment and surveillance may undergo an optional tissue biopsy (tumor and lymph node, if available) for correlative studies, which will require a separate ICF signature (see Section 4.5.1). A blood sample will also be collected at the time of disease progression/recurrence.

All patients will enter Survival Follow-up, which will cover new anti-cancer treatment, DFS, and OS for up to 3 years after the last dose of atezolizumab (See [Appendix 2](#) for details regarding time in Survival Follow-up).

